1. May participate in any study interaction or intervention (Including screening, consenting, and study activities)

AND/OR

2. You obtain any data/specimens about (regardless of identifiability)

at VCU and at other sites under the VCU IRB's oversight. See the help text for additional guidance.

100

2. If this is a multi-Center Project, what is the maximum anticipated number of subjects across all sites?

N/A

3. * Provide justification for the sample size by explaining how you arrived at the expected number of participants and why this number is adequate for answering the research questions:

This study manipulates e-cigarette flavor and nicotine flux systematically, testing the hypothesis that abuse liability will be related directly to flux or flavor among a sample of cigarette smokers. Previous studies using this type of design are limited.

Thus, we calculated a sample size to achieve a power of >0.80 with $\alpha < 0.05$ and assuming a small effect size (Cohen's $f=0.20$) and moderate repeated measures correlation ($r=0.5$) in a repeated measures ANOVA with nicotine flux as within-subjects factors ($N=32$; GPower).

In this study, 36 cigarette users will attend the lab for 4 sessions: 1) own brand cigarette (always the first session), 2) NJOY Ace 2.4% nicotine ECIG (Menthol and Classic Tobacco flavor), 3) NJOY Ace 5.0% nicotine ECIG (Menthol and Classic Tobacco flavor), and 4) NJOY Daily ECIG 6% nicotine (Menthol and Extra Rich Tobacco).

We hypothesize that flux will be positively associated with willingness to pay (drug purchase task) and willingness to substitute e-cigarettes for own brand cigarettes (cross-product drug purchase task), and inversely to price sensitivity (drug purchase task) for all smokers.

We hypothesize that within class, menthol flavored products will be positively associated with willingness to pay (drug purchase task) and willingness to substitute e-cigarettes for own brand cigarettes (cross-product drug purchase task), and inversely to price sensitivity (drug purchase task) for all smokers.

It is possible that we would consent up to 100 participants in order to obtain 36 participants who complete the entire study.

4. * List the study inclusion criteria:

All participants must be healthy (determined by self-report), at least 18 years old (verified by photo ID), willing to provide informed consent, and attend the lab. Participants must agree to use designated products according to the study protocol.

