Participants who have already consented to participate in the CSTP registry may be contacted via phone or e-mail and told about this study. Individuals who are participants in other, ongoing CSTP studies (participants with whom we have a pre-existing relationship) may be verbally referred to this study and directed to either call the laboratory or visit the website indicated on the advertisements, if they are interested.

Participants who are eligible and who choose to enroll may be contacted via text for appointment reminders if they agree (see scripts).

6. * Does this study have a separate protocol document (i.e. a multisite or sponsor's protocol) that contains a detailed description of the study's methodology?

☐ Yes

☒ No

7. * Since a separate protocol document is not uploaded, describe the proposed research using language understandable to those IRB committee members whose expertise is not scientific. The description must include:

- 1. A statement explaining the study design**
- 2. A detailed description of all the procedures that will be followed to carry out the study, preferably in sequential order, and in sufficient detail that the study's methods could be replicated**
- 3. The schedule and frequency of when and how procedures will be conducted (e.g. in person, online, phone, paper, etc.)**
- 4. A description of all research measures/tests/interventions that will be used, including analyses/tests conducted on specimens/biological samples (if applicable)**

See the help text for additional guidance

Overview. This study involves 36 cigarette users who will complete 4, within-subject, laboratory sessions that differ by the product used: 1) own brand cigarette, 2) NJOY Ace 2.4% nicotine ECIG (Menthol and Classic Tobacco flavor), 3) NJOY Ace 5.0% nicotine ECIG (Menthol and Classic Tobacco flavor), and 4) NJOY Daily ECIG 6% nicotine (Menthol and Extra Rich Tobacco). The first condition for all subjects will be their own brand cigarette which is completed at the conclusion of the in-person screening session or scheduled immediately following (if the participant is unable to complete this condition at the in-person screening session). The subsequent three sessions will be assigned using a Latin-square following enrollment and within each session participants will sample and evaluate two flavors of each session's product (session flavor order is incorporated into the Latin-square condition order assignment).

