Procedure. Following the in-person screening procedure and confirmation of eligibility, participants will be asked to complete 4 sessions the first of which will begin immediately following the in-person screening (or a day/time that is more convenient for the participant). Subsequent sessions must be scheduled at least 48 hours apart. Participants are not required to abstain from nicotine/tobacco (as we are not testing the ability of these products to suppress abstinence related symptoms or measure acute self-administration behavior), food, or caffeine prior to any session.

Of note, research staff will use Zoom, as an intercom to communicate with participants whenever possible during sessions.

At the start of the session, participants will be asked about symptoms experienced since their last visit (with the exception of session 1, if completed at the in-person screening session; see Presession symptom Checklist). Answers given about respiratory and gastrointestinal symptoms will be compared to the participants' previous answers, and if any symptoms have become more frequent or more severe, the medical monitor and/or study nurse will be asked to review the symptoms. In some cases, we may contact [name] to determine if a session can proceed.

Next, participants will have their breath tested (expired carbon monoxide [CO]) and physiologic data collection will begin. We will check blood pressure once at the beginning of the session and again at the end. Heart rate will be measured continuously throughout the session. Immediately after session onset, participants will have a 30-minute rest period.

During rest periods, participants will not be allowed eat or drink outside beverages, but we will provide water to drink and they are invited to use their phone, read books/magazines, or watch movies that we provide to them.

After the 1st rest period, participants will complete subjective measures 1. Immediately after completing subjective measures 1, participants will sample the session-specific product (5 self-directed ECIG/own brand cigarette puffs over 10 minutes). After sampling is complete they will complete subjective measures 2. Ten minutes after their sampling has been completed, they will complete the DPT/CP-DPT. The DPT/CP-DPT takes approximately 10 to 15 minutes to complete. Please note at session 1, only the DPT will be completed, blood pressure will be checked, physio data collection will end, and then the session will end.

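### The stated N=32 for power above 0.80 does not follow from its own inputs for any flux factor in the design; 36 completers just meet the four-condition requirement and give 0.73 for the three-level ECIG flux test

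*Combined protocol and SAP*

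**What the plan says.** The sample-size paragraph (Study Population, item 3) opens with the study "testing the hypothesis that abuse liability will be related directly to flux or flavor". It gives one calculation, meant to "achieve a power of >0.80 with $\alpha < 0.05". Its inputs are a Cohen's f of 0.20, which the plan calls small, and r=0.5 between measurements on the same person. The test and the resulting number are given as follows: "in a repeated measures ANOVA with nicotine flux as within-subjects factors ($N=32$; GPower"). Neither the number of repeated measurements nor a nonsphericity correction is given.

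The same item then says that "36 cigarette users will attend the lab for 4 sessions" and allows up to 100 consents to reach 36 completers. Study Procedures, item 7 (Recruitment and Enrollment) replaces non-completers until the target is met. The step from 32 to 36 is not explained.

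The level counts come from elsewhere in the protocol:

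- **Aim 1** (Background, Rationale and Goals, item 3) compares own brand cigarettes with three tobacco-flavor ECIGs that differ in flux. That is four conditions, three of them ECIG flux levels. The Overview in Study Procedures, item 7, agrees: "36 cigarette users who will complete 4, within-subject, laboratory sessions that differ by the product used".
- **Aim 2** compares menthol with tobacco inside each of three ECIG classes.
- **The CP-DPT** has no own brand measurement: "Please note at session 1, only the DPT will be completed" (item 7, Procedure).

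The Data analysis paragraph of item 7 excludes nonsystematic purchase-task data when elasticity is estimated. It also provides for sphericity adjustments and for Tukey or Bonferroni follow-up tests.

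**The concern.** With effect size, correlation, alpha and target power all printed, the required N depends only on the number of repeated measurements and on epsilon. A figure of 32 followed by a planned 36 looks like a requirement with four participants to spare. If 32 is too low for the factors actually tested, that apparent reserve does not exist, and some flux hypotheses do not have the power claimed for them.

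This matters most for substitution on the CP-DPT, which item 3 names as a flux hypothesis and which has one condition fewer than the DPT. The flavor question is introduced in the same paragraph but has no calculation of its own.

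**Working it through.** **Inputs** (Study Population, item 3): f=0.20, r=0.5, alpha=0.05, target power above 0.80. The number of levels m is taken from the aims and procedures. Epsilon is not stated; 1 (sphericity) is used unless noted.

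**Formula** (G*Power, repeated measures, within factors): noncentral F with λ = N·m·f²·ε/(1−r), df1 = (m−1)ε, df2 = (N−1)(m−1)ε. With the stated inputs and ε=1, λ = N·m·0.04/0.5 = 0.08·N·m.

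**Can 32 be reproduced?**

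| Measurements m | Smallest N for 0.80 | Power at N=32 | Power at N=36 |
|---|---|---|---|
| 2 (one flavor pair) | 52 | 0.59 | 0.65 |
| 3 (ECIG flux levels) | 42 | 0.68 | 0.73 |
| 4 (Aim 1 conditions) | 36 | 0.75 | 0.81 |
| 5 | 32 | 0.81 | 0.86 |
| 6 (ECIG product-flavor cells) | 28 | 0.86 | 0.91 |
| 7 (those cells plus own brand) | 26 | 0.90 | 0.93 |

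Only m=5 has 32 as its minimum (0.814 at 32; 0.799 at 31), and the design has no five-level factor. An epsilon below 1 does not help at m=3 or 4, because it raises the required N (m=4, ε=0.8: 42). At m=4, a minimum of 32 would need r of about 0.55, not 0.5.

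**Four conditions, at the planned 36.** λ = 0.08·36·4 = 11.52, df 3 and 105, power 0.808. At 35 evaluable, λ = 11.20, df 3 and 102, power 0.795. One participant lost from a complete-case analysis therefore takes the test below 0.80. Replacement covers non-completers; nothing in the plan replaces a completer whose purchase data are nonsystematic. As an assumed sensitivity value, ε=0.75 gives 0.72 at 36.

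**Three ECIG flux levels, tobacco flavor, at 36.** λ = 0.08·36·3 = 8.64, df 2 and 70, power 0.733. With no CP-DPT in session 1, its Aim 1 flux comparison can only take this form.

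**Averaging flux over both flavors.** Keep f=0.20 in single-cell SD units and r=0.5 between different products, and let s be the correlation between the two flavors of one product. Then λ = N·m·f²/((1+s)/2 − 0.5) = 4.32/(s/2) = 8.64/s. For s = 0.5, 0.7, 0.8 and 0.9, power at 36 is 0.96, 0.88, 0.83 and 0.78. The documents give no value for s.

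**One flavor contrast within a class, at 36.** With two levels, f=0.20 is a difference of 0.4 SD. With r=0.5 the SD of the difference is √(2·0.5) = 1, so dz=0.40. Power is 0.65 at alpha 0.05 and 0.46 at 0.05/3.

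**Flavor main effect over three classes, at 36.** If the class-specific differences correlate c, dz = 0.4/√((1+2c)/3). For c = 0, 0.3, 0.5 and 0.7, power is 0.98, 0.89, 0.82 and 0.74.

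**The case against.** The strongest reply is that the study recruits 36, not 32, and replaces dropouts, so the headline Aim 1 comparison has 0.81. That stands. A reader might infer from the error that Aim 1 as a whole is underpowered. The documents do not support this: on the DPT, with sphericity and all 36 evaluable, the four-condition test meets its target.

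A reader might also conclude that five measurements were entered by mistake. Item 3 does not give the number, so that remains an inference. The target is worded as exceeding 0.80, and 32 also exceeds it for six or seven measurements, which match the ECIG cells without and with own brand. This does not rescue 32, because the paragraph names flux as the factor, and flux has three levels, or four with own brand.

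A third tempting reading is that flavor has less power than claimed. No power is claimed for flavor; the gap is an omission. The hypothesis in Background, Rationale and Goals, item 2, is worded across classes, and a pooled test may be well powered. Aim 2 and the item 3 hypothesis, however, are framed within class.

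Finally, both flavors are measured in every ECIG session, so 0.73 uses half the ECIG data. This is fair for the item 3 flux hypothesis, which is not limited to one flavor. It does not change Aim 1, which is limited to tobacco flavor, and the gain depends on an unstated correlation. The exclusion rate and epsilon are also unstated, so figures that use them are sensitivities, not predictions.

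**Conclusion.** The concern holds in this limited form. N=32 for power above 0.80 cannot be obtained from the printed inputs with three or four flux levels; the requirements are 42 and 36. The planned 36 equals the four-condition minimum and leaves no reserve, so excluding even one participant's elasticity data puts a complete-case test under 0.80. A mixed model or multiple imputation, both allowed by the plan, could recover part of that loss. The three-level tobacco-flavor flux test has 0.73 at 36, short of the stated target, and this covers the only Aim 1 flux test available to the CP-DPT. Flavor is unsized: 0.65 per within-class contrast, 0.46 after Bonferroni, and 0.74 to 0.98 for a main effect across classes.

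These figures assume sphericity unless noted, f=0.20 for every effect, r=0.5 between conditions, and 36 evaluable. They do not show that the planned sample is wrong for the four-condition test.

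**What to change.** Revise the paragraph in Study Population, item 3, without adding participants:

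1. Replace N=32 by N=36 for the four-condition test, and state the number of measurements and the epsilon assumed.
2. Say that 36 carries no margin: 0.81 with all evaluable, 0.795 with 35.
3. Report 0.73 for the three-level tobacco-flavor flux test, including the CP-DPT. If flux is to be averaged over flavors, say so and state the correlation assumed.
4. Report 0.65 for each within-class flavor contrast and 0.46 with Bonferroni over three classes.

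Two further steps are optional. A one-degree-of-freedom trend across the ECIGs has 0.82 at 36 if the effect is linear over equally spaced levels: means −d, 0, d with f=0.20 give d = 0.20·√1.5 = 0.245, so the end-to-end dz is 0.49. The documents give no flux values to support equal spacing. A flavor test pooled over classes, followed by the within-class contrasts, depends on the correlation between class differences.

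The cost is protocol wording and some less favorable power figures. Recruitment and procedures do not change.

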Participants must smoke cigarettes at least 3 days per week and on those days at least 1 cigarette smoked per day.

Participants must have a 'positive' cotinine cassette result to verify nicotine use.

Please note that beginning July 1, 2020, per HB1570 Virginia law "Provides an exception to the law prohibiting possession of tobacco products, nicotine vapor products, or alternative nicotine products by a person less than 21 years of age when such possession is part of a scientific study being conducted by an organization for the purpose of medical research to further efforts in cigarette and tobacco use prevention and cessation and tobacco product regulation, provided that such medical research has been approved by an institutional review board pursuant to applicable federal regulations or by a research review committee."

5. * List the study exclusion criteria:

Individuals with the following self-reported current, diagnosed medical condition(s) will be excluded automatically: uncontrolled high blood pressure (via self-report or observed at screening; BP must be less than 160/100), heart-related conditions (e.g., recent heart attack/stroke, coronary heart disease), severe immune system disorders (e.g., HIV/AIDS, multiple sclerosis), respiratory disorders (e.g., COPD, asthma), kidney diseases, liver diseases (e.g., cirrhosis), or seizures.

Individuals with other self-reported current, diagnosed medical conditions (e.g., diabetes, thyroid disease, Lyme disease) will be considered for exclusion after consultation with the PI and medical monitor. We ask a variety of questions about participants' medical conditions that are not necessarily exclusionary in order to be able to consult with

the medical monitor about these conditions. Participants with any medical condition/medication that may affect participant safety, study outcomes, or biomarker data will be excluded based on these consultations.

Individuals with current, diagnosed, psychiatric conditions that are uncontrolled will be excluded. A controlled psychiatric illness is defined as one where the individual is taking medication and/or receiving other treatment (e.g., psychotherapy). In addition, individuals who have been to the ER and/or been hospitalized for a psychiatric condition in the past year will be excluded.

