In sessions 2 and 3 and 4, after completing the 1st DPT/CP-DPT, participants will start the 2nd 30-minute rest period. After the rest period, participants will complete subjective measures 3. Immediately after subjective measures 3, participants will sample the other session-specific product (5 self-directed ECIG puffs over 10 minutes). After sampling is complete they will complete subjective measures 4. Ten minutes after their sampling has been completed, they will complete the DPT/CP-DPT.

After completing the 2nd DPT/CP-DPT, blood pressure will be checked, physio data collection will end, and participants will be paid for their time.

The study procedures for session 1 should take no more than 70 minutes or 1.2 hours, and for sessions 2 and 3 and 4 should take no more than 140 minutes or 2.3 hours.

Please note there can be some variability in the session times due to participant behavior (i.e., taking shorter/longer than expected to complete measures/tasks).

Session Timeline:

0m – eCO Check; Physiologic data collection begins, additional questions asked.
5m – Begin 30m Rest Period 1
35m – Subjectives 1
40m – Sample Product 1 (puffs)
50m – Subjective 2
60m – 1st DPT/CP-DPT
75m – Begin 30m Rest Period 2 / Physiologic data collection ends; Session 1 end
105m – Subjectives 3
110m – Sample Product 2 (puffs)
120m – Subjective 4
130m – 2nd DPT/CP-DPT
140m – Physiologic data collection ends; Session 2/3/4 end

Note: Product sampling will consist of 5 self-directed sample puffs for own brand cigarettes or ECIG conditions taken over 10 minutes.

Measures.

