3. The ECIG liquid used may contain less or more nicotine than participants normally ingest, but these effects are unlikely in individuals who use cigarettes regularly. Participants also might experience side effects from products that contain nicotine such as acute increases in heart rate and blood pressure, sweating, lightheadedness, dizziness, nausea, and nervousness.
4. The Centers for Disease Control and Prevention advises that e-cigarette, or vaping products are unsafe for youths, young adults, or women who are pregnant. Adults who do not currently use tobacco products should not start using e-cigarette, or vaping, products. If you use e-cigarette products, monitor yourself for all of these symptoms and promptly seek medical attention if you have concerns about your health.
 - a. Some people who use e-cigarettes have reported experiencing seizures. Some of these individuals reported a prior history of seizures or using other substances at the same time as their e-cigarette.
 - b. In some cases, e-cigarette use has led to respiratory illnesses such as difficulties breathing, shortness of breath, cough, and/or chest pain before hospitalization. In some cases, e-cigarette use has led to death, although most of these cases have been related to vaping THC.
 - c. In some cases, symptoms of mild to moderate gastrointestinal illness such as nausea, abdominal pain, vomiting, diarrhea, or fevers or fatigue have been reported.
5. The use of e-cigarettes may include other side effects/risks such as a sore or scratchy throat and headache.
6. There is some risk of loss of confidentiality.
7. The procedures in this research are known to hurt a pregnancy or fetus in the following ways: cigarette smoking during pregnancy raises risk for pre-term birth, birth defects, and bleeding during pregnancy/delivery; cigarette smoking also can negatively impact fertility. The research may also hurt a pregnancy or fetus in ways that are unknown. These may be a minor inconvenience or may be so severe as to cause death. Participants should not be or become pregnant or father a baby while on this research study.
8. In addition to these risks, this research may hurt participants in ways that are unknown. These may be a minor inconvenience or may be so severe as to cause death.

2. * Describe how each of the risks/harms/discomforts identified above will be minimized:

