During the sessions, if the participant reports experiencing small droplets of ECIG liquid during inhalation, we will immediately replace the product they are using in the session.

We will inform participants of the other ECIG-related side effects during the informed consent process. These risks are minimized by limited exposure to ECIGs in study sessions. We do not anticipate participants taking more than 5-10 total puffs per session. The risk of overexposure to nicotine from the ECIGs administered is also minimized by enrolling

current cigarette smokers (cigarettes are among the most efficient and effective nicotine delivery systems currently marketed).

The risk of seizures is minimized by excluding participants with any history of seizures, and by having a full-time RN available, as well as monitoring of vital signs. In addition, some of the reported seizures occurred in users who were using other substances such as marijuana or amphetamines--the risk of seizures in this study is reduced as we are administering nicotine and no other substances.

The risk of respiratory illnesses related to ECIG use is minimized by the limited ECIG use that occurs in each session. Participants are expected to take no more than 5-10 puffs of either their own brand CIG or session-specific ECIGs at each session. Participants are informed about recent reports of ECIG-related respiratory illnesses and are informed that the CDC has advised people to stop vaping. Participants are also advised to monitor themselves for symptoms and to seek medical attention if they have concerns. In addition, we will ask about respiratory and gastrointestinal symptoms at screening and before each session begins. Answers given at the beginning of each session will be compared to the participants' previous answers, and if any symptoms have increased, [name] will be asked to review the symptoms. In some cases, we may contact [name] to determine if a session can proceed.

We recruit individuals aged 18 + who use nicotine-containing products at similar or higher daily/weekly frequencies that they would be exposed in the laboratory setting. Our protocol ensures that study-related nicotine/tobacco exposure is similar to or less than what participants may expose themselves to as part of their ordinary life.

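### The seizure exclusion is written for current, diagnosed conditions, but the risk section relies on excluding anyone with any history of seizures

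*Combined protocol and SAP*

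**What the plan says.** Study Population, item 5, sets out three layers of medical exclusion.

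- **Automatic.** The lead-in is "Individuals with the following self-reported current, diagnosed medical condition(s) will be excluded automatically". The list that follows closes with "kidney diseases, liver diseases (e.g., cirrhosis), or seizures".
- **By consultation.** Other current, diagnosed conditions "will be considered for exclusion after consultation with the PI and medical monitor".
- **Safety catch-all.** "Participants with any medical condition/medication that may affect participant safety, study outcomes, or biomarker data will be excluded based on these consultations".

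Item 4 of the same section adds a general requirement that participants report being healthy. It does not mention seizures.

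Risks, Discomforts, Potential Harms and Monitoring, item 2, describes how the seizure risk is handled: "The risk of seizures is minimized by excluding participants with any history of seizures". It goes on to cite the availability of a full-time nurse, vital-sign monitoring, and the fact that the study gives nicotine and no other substance.

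Item 1 of that section, and Behavioral Intervention/Task Details, item 2, say of people who reported seizures with e-cigarettes: "Some of these individuals reported a prior history of seizures or using other substances at the same time as their e-cigarette".

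**The concern.** The rule staff apply at enrollment is narrower than the safeguard the risk section claims. A current, diagnosed condition and any past seizure define different groups. The people in between have had a seizure at some point but carry no current diagnosis. The risk section says they are excluded; the eligibility section, read literally, does not exclude them automatically.

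What is at stake is participant safety. The protocol names prior seizures as a feature of some reported e-cigarette seizure cases. Of the seizure measures listed in the risk section, the history exclusion is the only one that acts before a person is enrolled. The nurse and the vital-sign monitoring come into play only once the participant is in the laboratory.

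**Working it through.** The plan gives no figure for this point, so there is nothing to reproduce. The check compares the texts and then counts the exposure.

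**1. What the automatic criterion covers (Study Population, item 5).** Three qualifiers govern the list: self-reported, current and diagnosed. Seizures are the last item and have no wording of their own extending them to past events. Elsewhere the eligibility section states a look-back period where it wants one: the past year for psychiatric emergency visits or hospitalization, and the past month for illegal drug use. Seizures have none.

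**2. What the risk section claims (Risks, item 2).** Any history of seizures, with no limit on time or diagnosis.

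**3. Whether anything reconciles the two.** Items 4 and 5 of Study Population contain no criterion worded as any past seizure, and no other section of the application supplies one.

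**4. What happens to a person with a past seizure and no current diagnosis.**

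- Automatic list: not excluded on a literal reading.
- Consultation route: introduced for current, diagnosed conditions, so this person may never be referred.
- Safety catch-all: could exclude, but only as an outcome of those consultations.
- Healthy by self-report: someone with a remote seizure could honestly meet it.

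None of these guarantees the exclusion that the risk section describes.

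**5. Other protections bearing on seizures.** The pre-session symptom comparison (Study Procedures, item 7) concerns respiratory and gastrointestinal symptoms. Risks, item 6, states that there are no prespecified criteria for stopping or changing the study on safety grounds. The drug-use exclusion addresses the other feature named in the reported cases, use of other substances. It still admits cannabis use on up to 15 days and alcohol use on up to 25 days of the past 30.

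**6. Exposure of anyone admitted (Study Procedures, item 7).** Each e-cigarette session has two sampling periods. In the first, participants "sample the session-specific product (5 self-directed ECIG/own brand cigarette puffs over 10 minutes"); in the second, "participants will sample the other session-specific product (5 self-directed ECIG puffs over 10 minutes").

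- Per session: 2 flavors × 5 puffs = 10 e-cigarette puffs.
- Three e-cigarette sessions: 3 × 10 = 30 e-cigarette puffs, at 2.4%, 5.0% and 6% nicotine, in sessions at least 48 hours apart.

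**7. Room for the fix (Study Population, item 3).** Up to 100 consents are allowed for 36 completers: 100 − 36 = 64. Those 64 must also cover every other screen failure and dropout.

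**The case against.** The strongest reply is that both statements belong to one IRB application, with no separate protocol document. The risk section states the wider exclusion as something the study does, so the stricter rule is already in force and the eligibility list is merely shorthand. The list is also drafted loosely. It includes recent heart attack or stroke, which are past events, and blood pressure observed at screening, which is not self-reported. Seizures are named as events, not as a seizure disorder, so a past seizure can be read into the item. The catch-all sentence is not itself confined to current conditions. Finally, the participants are established smokers whose study nicotine exposure is described as no greater than usual, and the screening forms, which may already ask about any past seizure, are not available.

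Much of this is fair. The wider reading is possible, and the risk section shows it is what the investigators intend. No screening failure has been shown, only a difference in wording. Low exposure limits the likely harm.

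The reply does not remove the gap. Eligibility is decided from the inclusion and exclusion criteria, and a reader has to go to the risk section to learn that one item means more than its lead-in says. Even the heart attack and stroke example carries its own limit of recency, whereas seizures carry no wording about the past at all. The remaining routes depend on a referral being made and on the judgment that follows, which falls short of a categorical exclusion.

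**Conclusion.** The point holds. Applied as written, the exclusion criterion can admit people whom the stated safety measure says are excluded. It should be corrected, as a matter of participant safety; the aims, sample size and analysis are unaffected.

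Its size cannot be expressed as a number of participants or events, because the documents give no prevalence of past seizures and no seizure rate, and none is assumed here. The conclusion rests on reading the lead-in as governing every item in its list. Confidence is moderate, because the list is loosely drafted and the screening questions cannot be seen. If those questions already ask about any past seizure and staff exclude on the answer, no one is wrongly enrolled in practice, and the defect is confined to the protocol text.

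**What to change.** In Study Population, item 5, take seizures out of the list governed by the current-and-diagnosed lead-in. Add a separate automatic exclusion for anyone who reports ever having had a seizure, whether or not a diagnosis was made. Then check that the registry and baseline screening questions ask about any past seizure, and reword them if they ask only about current conditions.

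The cost is one line in a minor IRB amendment and a check of the forms. A few people with a remote or provoked seizure may be turned away. They would count against the 64 consents beyond the 36 completers, and they are people the risk section already says are excluded, so no exclusions are added beyond those intended.

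Narrowing the risk section to match the present criterion would also remove the inconsistency, but it would give up the only listed seizure measure that acts at eligibility and is not recommended.
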